#### **Pooling of Investigator Centers**

All subjects in this study come from one investigational center.

#### **Baseline Values**

Baseline values are from screening/baseline visit for all measures, except CAPS-5 and C-SSRS. Baseline CAPS-5 will be assessed, during screening (pre-study), no more than 8 weeks before the first experimental session. This allows adequate washout of at least five half-lives of pre-study psychiatric medications and active metabolites, plus one week for stabilization. If CAPS-5 is completed outside of this window for a participant, the PI will consult the CRA and Medical Monitor to determine if the Baseline CAPS should be repeated. For C-SSRS, pre-enrollment scores will be used as a measure of 'lifetime' suicidal ideation and behavior, and preparatory session 2 (visit 2) prior to drug administration will used as 'baseline.' If a subject was not administered the C-SSRS at preparatory session 2 (visit 2), then 'baseline' scores will be visit 3 pre-drug C-SSRS observation.

## **Subject Disposition and Dosing Summary**

All subjects enrolled in the study (i.e., who sign informed consent and complete inclusion/exclusion criteria) will be included in the summary of subject disposition and accountability. No inferential statistical tests will be performed. The tabulation of number of subjects will be displayed for all subjects in the Safety population, in the mITT population, and

in the PP population. The number and percent of subjects who completed or discontinued the study will be reported along with reasons for early termination. Percents will be defined as the number of participants who completed, or number discontinued, over the total number of subjects in the total study sample, and separately, for PTSD+ participants and CSO participants. The timepoint of doses and total MDMA (mg) administered will be summarized for the Safety, mITT and PP populations for the total sample and by PTSD+ participants and CSO participants.

## **Demographics and Baseline Characteristics**

Subject demographic data and baseline characteristics will be summarized descriptively overall and by PTST+ participants and CSO participants. The demographic data and baseline characteristics will be summarized for the mITT.

#### **Prior and Concomitant Medications**

The number and percent of subjects who took medications prior to and after signing informed consent will be summarized descriptively for the total sample and by PTSD+ participants and CSO participants. Concomitant medications will be summarized similarly. Prior and concomitant medications will be summarized for the Safety Population. Psychiatric medications will be coded to common drug classes and terms.

# **Efficacy Analyses**

For all primary, secondary, and exploratory endpoints descriptive statistics (n, mean, standard deviation, median, range, effect size (for measures of interest), or frequencies and percentages where appropriate) will be provided for the total sample and by PTSD+ participants and CSO participants.

Effect size (Hedges' g) will be determined by calculating the mean difference pre- and post-treatment divided by the pooled weighted standard deviations for means at baseline and follow-up [3].

Hedges' 
$$g = (M_1 - M_2) / SD*_{pooled}$$

Where:

- $M_1 M_2 = \text{difference in means}$
- SD\*pooled = pooled and weighted standard deviations

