In addition, the treatment has been shown to lead to improvements in intimate relationship functioning and significant improvements in intimate partners' mental health [33, 34]. Research also suggests that CBCT for PTSD improves parenting satisfaction and efficacy among those with children [13], and that regardless of initial levels of intimate relationship functioning, individuals with PTSD profit from the treatment [35].

This is a Phase 1/2 open-label experimental medicine study in 10 dyads including a participant who has been diagnosed with PTSD for at least 6 months and a significant other participant (i.e., intimate or non-intimate person) who does not have a current diagnosis of PTSD and significant other experiencing associated psychological distress as assessed per the V-codes in the DSM-5. The dyad members will be referred to individually as the PTSD+ participant (diagnosed with PTSD) and the CSO Participant (concerned significant other). Eligible and enrolled participants will undergo a 2-month course of psychotherapy as a dyad that includes CBCT for PTSD integrated with MDMA-assisted psychotherapy. The CBCT sessions, as described in Monson and

Fredman's (2012) manual [1] will be integrated with elements of the Treatment Manual for MDMA-assisted Psychotherapy in order to modify CBCT to incorporate MDMA as a catalyst for the therapeutic process [2]. The integration of these treatments will provide the researcher with a consistent psychotherapy approach and test an experimental form of drug-assisted psychotherapy. This study is designed to obtain estimates of effect size for safety and efficacy. This study is also intended to contribute to the development of a manualized psychotherapeutic approach to this potential treatment. Since this is the first time that CBCT is being combined with MDMA-assisted psychotherapy for PTSD, we are interested in gathering preliminary information about the blending of these two therapeutic approaches.

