12.0 Data Analysis

Key Personnel, MAPS, and the biostatistician will agree on a Statistical Analysis Plan at the beginning of the study. The biostatistician will perform an Intent to Treat (ITT) analysis using repeated measures Analysis of Covariance (ANCOVA) to compare demographics and all available data from any participant receiving at least one Experimental Session and completing follow-up assessments from all participants, even if they withdraw from the allocated treatment prior to the Primary Endpoint.

This pilot study will test the impact of MDMA-assisted psychotherapy with CBCT for reducing PTSD and other psychological symptomology (e.g., depression) among a sample (N=10) of participants with PTSD. The primary measure will be a paired T-test of CAPS scores from Baseline to Primary Endpoint. In addition, to determine the strength of the treatment effect, pre to post (paired) mean differences effect size estimates will be calculated. Durability of effects will be examined by comparing changes from Baseline to the assessments at three and six months after the final Experimental Session using mixed-effects regression methods, which accounts for both missing data and the nesting of correlated longitudinal data within participants.

Effect sizes will be estimated for all outcome measures using Cohen's (1988) procedures (Cohen's d and small sample bias corrected Hedges' g) [194]. Effects on depression symptoms, psychological functioning, trauma-related beliefs, interpersonal closeness, and sleep quality will also be assessed for exploratory purposes. The biostatistician will conduct secondary analyses of self-report assessments using repeated measures ANCOVA. As a secondary outcome measure, weekly PCL-5 assessments will be conducted 15 times, starting at the second prep visit, weekly during treatment, and three follow-up assessments. To examine changes in PCL-5 over the 15 time points, the sponsor statistician will use linear mixed-effects regression with restricted maximum likelihood estimation, using weeks as a continuous variable. Measures of relationship satisfaction will be analyzed separately for participants with and without PTSD. Statistical significance will be determined based on $\alpha < .05$ for all tests other than the PCL-5, which will be a secondary measure for self-reported PTSD symptoms intended to support the CAPS.

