12.1 Statistical Power

This pilot RCT is the first study of its kind intended to establish preliminary effect size estimates of CBCT combined with MDMA-assisted psychotherapy for PTSD. In the absence of published effect sizes for this new treatment modality, effect sizes were estimated based on prior trials of these individual treatments. In a limited number of small pilot studies, CBCT for PTSD yielded paired-treatment effect sizes of g > 1.0 for improvements in PTSD on the primary outcome measure and co-morbid symptoms. The two completed controlled RCTs of MDMA-assisted psychotherapy for PTSD have yielded effect sizes of g > 1.0 for improvements in PTSD symptoms as well. Assuming that effect size of the combined treatment may be approximately 0.8, estimated power for a within-subject analysis with a significance level of .05 based on a 2-tailed test, is 62% for a sample size of 10 participants for the primary measure, suggesting the potential for an underpowered design, but with some possibility of detecting a within-subject effect due to treatment. Statistical power estimates were not available for secondary and exploratory measures, as they were previously not used in sponsor-supported studies.

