## 1. Primary Efficacy Analyses

The primary efficacy evaluation is a paired t-test of CAPS-5 Total Severity scores at baseline and the primary endpoint (visit 16) at an alpha level of 0.05. If the parametric assumptions for t-test analyses are not met, the analogous nonparametric methods will be used (Wilcoxon Rank-Sum).

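### The SAP's printed formula for Hedges' g lacks the small-sample correction that the protocol promises, and no confidence interval is planned for the effect size or the mean CAPS-5 change

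*SAP*

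**What the plan says.** Protocol 2.1 gives the purpose: "This study is designed to obtain estimates of effect size for safety and efficacy". Protocol 5.1.1 makes change in the CAPS total score the main source of that estimate. Protocol 12.0 says that effect sizes for all outcome measures will be "Cohen's d and small sample bias corrected Hedges' g".

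The SAP, under Efficacy Analyses, says that g is obtained by "calculating the mean difference pre- and post-treatment divided by the pooled weighted standard deviations for means at baseline and follow-up". It prints the equation (M1 − M2) / SD*pooled, explains the denominator only as a pooled, weighted SD, and cites a methods paper. No correction factor or degrees of freedom appears, and Cohen's d is not mentioned. The statistics to accompany g are n, mean, SD, median and range. SAP 6.0 adds p-values to four decimals. The primary analysis is a paired t-test of CAPS-5 at baseline and visit 16. Neither document mentions a standard error or confidence interval for g or for the mean change.

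**The concern.** Pooling or weighting SDs does not correct for small samples. As printed, the SAP's statistic is the uncorrected standardised difference under the name Hedges' g, which conflicts with protocol 12.0. With ten pairs the uncorrected value is too far from zero on average.

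The absence of an interval matters more. When the effect size is itself the product of the study, a bare point value does not show how little ten pairs determine. SAP 2.0 expects the results to inform the planning of a bigger trial, so a user of the estimate needs its uncertainty stated.

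**Working it through.** **Inputs.** n = 10 PTSD+ participants, effect size 0.8, two-sided 5% test (protocol 12.1). The SAP's formula is as printed. Assumed, because the documents do not give them: equal SDs at the two time points, and r from 0.3 to 0.9.

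**1. The plan's own figure.** Protocol 12.1 starts with "Assuming that effect size of the combined treatment may be approximately 0.8" and states that power "is 62% for a sample size of 10 participants for the primary measure". A paired t-test with 9 df and noncentrality 0.8 × √10 = 2.53 has power 61.6%, so the 62% reproduces. There, 0.8 is the mean change divided by the SD of change. The SAP divides by the pooled time-point SD. With equal SDs,

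standardised change on the SD-of-change scale = g / √(2(1 − r)),

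so the two scales agree only at r = 0.5. An effect of 0.8 on the SAP's scale is 0.676 on the power scale at r = 0.3 (power 48%) and 1.033 at r = 0.7 (power 83%). Any repair therefore has to name the standardiser.

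**2. Bias of the printed formula.** The expected value of the uncorrected estimate is about the true value divided by J, where J = Γ(df/2) / [√(df/2) Γ((df − 1)/2)] ≈ 1 − 3/(4 df − 1). For the SD of change, df = 9 and J = 0.914. For the pooled SD of two correlated time points, the effective df is 2(n − 1)/(1 + r²) = 18/(1 + r²). Simulation of the SAP's formula (400,000 samples per setting, true effect 0.8) checks this:

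| r | df | J | 1/J − 1 | simulated mean | sampling SD |
|---|---|---|---|---|---|
| 0.3 | 16.5 | 0.954 | 4.8% | 0.8390 | 0.427 |
| 0.5 | 14.4 | 0.947 | 5.6% | 0.8425 | 0.378 |
| 0.7 | 12.1 | 0.936 | 6.8% | 0.8524 | 0.325 |
| 0.9 | 9.9 | 0.922 | 8.4% | 0.8657 | 0.266 |

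The average excess is 0.839 − 0.8 = 0.039 to 0.866 − 0.8 = 0.066, that is 4.9% to 8.2%. Relative to the sampling SD it is 0.039/0.427 = 0.09 to 0.066/0.266 = 0.25.

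**3. Does the matching df repair it?** Mean × J gives 0.8390 × 0.954 = 0.800, 0.8425 × 0.947 = 0.798, 0.8524 × 0.936 = 0.798 and 0.8657 × 0.922 = 0.798. A mismatched df does less well. At r = 0.7, df = 18 (J = 0.958) leaves 0.8524 × 0.958 = 0.817, and df = 9 gives 0.8524 × 0.914 = 0.779.

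**4. Width of the missing interval.** For an observed 0.8 on the SD-of-change scale, t = 2.53 with 9 df, and inverting the noncentral t gives 95% limits of 0.07 to 1.50. For an observed SAP g of 0.8, rescaling by √(2(1 − r)) gives roughly −0.04 to 1.60 at r = 0.3 and 0.18 to 1.39 at r = 0.7. On either scale the interval is more than one unit wide, against a bias of 0.04 to 0.07.

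**The case against.** The best defence is that the correction is implied. The SAP names the statistic Hedges' g, cites a methods paper, and says in its Introduction that it rests on the protocol's analysis plan. The SAP is dated 26 February 2016. The protocol that still promises the correction is Amendment 4 of 8 May 2017, so the later document has the right estimator. An analyst may well apply the correction, and the documents do not show that it would be left out. What stands is that the explicit equation disagrees with protocol 12.0, and that an implied correction leaves the df unstated. The sentence in SAP 4.0 that makes the protocol definitive introduces the design overview. If it does govern, the equation still needs editing.

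Three stronger readings are tempting, and the documents do not support them.

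- *Every reported effect will be too high, always in favour of treatment.* The bias is an average and is away from zero. A worsening is inflated equally, and a true zero is not biased. In the simulations 46% to 49% of estimates fell below the true 0.8. The SAP also limits effect sizes to measures of interest and reports the total sample as well, where both dyad members give n of about 20 and the bias is smaller.
- *The trial's precision is hidden.* For the primary outcome it can usually be rebuilt. With complete pairs, the exact p-value gives |t|, the SE is the mean change divided by |t|, and |t|/√n is the standardised change. For example, p = 0.0322 gives |t| = 2.53 and 2.53/√10 = 0.80. This fails if p is shown only as below 0.0001 (|t| above 6.59, standardised change above about 2.1) or if the non-parametric fallback is used. It is a reporting gap, and readers should not have to reconstruct the main result.
- *A later trial will be seriously missized.* SAP 2.0 mentions a larger study but gives no sizing rule, and both documents say that this pilot is not meant to lead to a registration study.

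**Conclusion.** The point holds on two counts: the SAP's equation contradicts protocol 12.0, and no interval is planned for the quantity that the study exists to estimate. The first costs about 5% to 8% on average in the magnitude of a non-zero effect at n = 10, given equal SDs and r between 0.3 and 0.9. Since that is at most about a quarter of one sampling SD, the missing interval is the more important omission. The primary paired t-test and its p-value are unaffected.

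**What to change.** In SAP Efficacy Analyses:

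- Replace the printed equation by g = J × d with J = 1 − 3/(4 df − 1), to agree with protocol 12.0.
- Name the standardiser and a matching df. If d uses the SD of change, df = n − 1. If the pooled time-point SD is kept, df = 2(n − 1)/(1 + r²) with the observed pre-post correlation r, which should then be reported.
- Report a 95% confidence interval for g on that same scale, and one for the raw mean CAPS-5 change.
- State on which scale the 0.8 in protocol 12.1 is meant, so that the observed g can be compared with it.

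This takes a few lines of SAP text and of code. It needs no new data and no change to the primary test. The only downside is a slightly smaller reported g: an uncorrected 0.80 becomes 0.80 × 0.947 = 0.76 on the pooled-SD scale at r = 0.5, or 0.80 × 0.914 = 0.73 on the SD-of-change scale.

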## 1. Primary Efficacy Analyses

The primary efficacy evaluation is a paired t-test of CAPS-5 Total Severity scores at baseline and the primary endpoint (visit 16) at an alpha level of 0.05. If the parametric assumptions for t-test analyses are not met, the analogous nonparametric methods will be used (Wilcoxon Rank-Sum).

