5.0 Methods

5.1 Measures

The following outcome, safety, and process measures will be used in the study. This study will utilize methods described in the Treatment Manual for conducting MDMA-assisted Psychotherapy combined with methods from the CBCT for PTSD manual. The integration of these manuals will provide the researcher with a consistent psychotherapy approach and test an investigational form of drug-assisted psychotherapy. The Treatment Manual is not intended to define all interactions that occur in the therapy. All psychotherapy sessions, including Experimental Sessions, may be recorded to audio and video, with all recordings preserved for research and training purposes.

Page 32 of 89

Table 4: Study Measures

Measure	Purpose	Administration	Time/ # of items	When	PTSD+ Participant	CSO Participant
Screening, Inclusion & Exclusion						
SCID for DSM-5- AXIS 1 only and then screening question for AXIS 2 modules (do modules if needed)	Screening	Interview	60 minutes	Baseline	Y	Y
Primary & Secondary Outcomes						
CAPS-5 Clinician Administered PTSD Scale for DSM-5	PTSD Severity	Interview	90 minutes	Baseline, Endpoint, LTFU 3, 6	Y	N
PCL (last month) PTSD Checklist for DSM-5	PTSD symptoms	Self-report	10-15 minutes	Baseline (with LEC), Endpoint, LTFU 3, 6	Y	Y (PCL- Participant)
PCL (since last visit) PTSD Checklist for DSM-5	PTSD symptoms	Self-report	10-15 minutes	Integrative Sessions, Midpoint	Y	Y (PCL- Participant)
PCL (since last week) PTSD Checklist for DSM-5	PTSD symptoms	Self-report	10-15 minutes	Visit 2	Y	Y (PCL- Participant)
BDI-II Beck Depression Inventory	Depression Symptoms	Self-report	5-10 minutes	Baseline, Midpoint, Endpoint, LTFU 3, 6	Y	Y
ERQ Emotional Regulation Questionnaire	Emotion regulation	Self-report	4-6 minutes	Baseline, Midpoint, Endpoint, LTFU 3, 6	Y	Y
IRI Interpersonal Reactivity Index	Compassion empathy, social functioning	Self-report	10 minutes	Baseline, Day after Experimental Sessions, Midpoint, Endpoint, LTFU 3, 6	Y	Y
PSQI Pittsburg Sleep Quality Index	Sleep Quality	Self-report	5-10 minutes	Baseline, Midpoint, Endpoint, LTFU 3, 6	Y	Y
PTGI Post Traumatic Growth Inventory	Growth after Trauma	Self-report	5-10 minutes	Baseline, Midpoint, Endpoint, LTFU 3, 6	Y	Modified for participant. Participant will rate the PTSD participant. Y
TAS-20 Toronto Alexithymia Scale	Emotion recognition, alexithymia	Self-report	5 minutes	Baseline, Midpoint, Endpoint, LTFU 3, 6	Y	Y

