#### 1.0 Introduction

This document presents a Statistical Analysis Plan (SAP) for MAPS study protocol MPVA-1, a Phase 1/2 open-label feasibility study exploring the safety and efficacy of combined MDMA-assisted pyschotherapy with Cognitive-Behavioral Conjoint Therapy (CBCT) for treating individulas with chronic treatment-resistent Posttraumatic Stress Disorder (PTSD) and a significant other with associated pyschological distress. This study is not intended to lead to a registration study.

The statistical plan described hereafter is an *a priori* plan based on the statistical analysis plans included in the study protocol. This SAP will be finalized prior to any inferential or descriptive analyses of data pertaining to the MAPS-sponsored MPVA-1 study. SAS programming may occur as study data accumulate in order to have analysis programs ready at the time data are locked and available for analysis. For the reasons stated here, the conduct of the study in the field is considered to be independent of any study outcomes that might materialize upon enactment of the currently proposed statistical plan.

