## 2. Secondary and Exploratory Efficacy Analyses

Efficacy of secondary and other exploratory outcome measures will be assessed at baseline, midpoint (visit 9), and primary endpoint (visit 16) to examine change in scores over time in the total sample, and separately, by PTSD+ participants and CSO participants.

For each model, a one-way repeated-measures ANOVA with post-hoc contrast comparisons will be conducted to test the effects of the treatment on: PTSD CAPS-5; Significant Others' Responses to Trauma Scale (SORTS); Posttraumatic Stress Disorder Checklist for the DSM-5 (PCL-5); Beck Depression Inventory-II (BDI-II); Emotion Regulation Questionnaire (ERQ); Pittsburgh Sleep Quality Index (PSQI); Posttraumatic Growth Inventory (PTGI); Toronto Alexithymia Scale-20 (TAS-20); Inventory of Psychosocial Functioning (IPF); Revised Conflict Tactics Scale (CTS-2); Trauma and Attachment Beliefs Scale (TABS); and Multiscale Dissociation Inventory (MDI). Relationship distress outcome measures include: Interpersonal Reactivity Index (IRI); Quality of Relationships Inventory (QRI); Miller Social Intimacy Scale (MSIS); Interpersonal Closeness Measure (IPC); and Couples Satisfaction Index (CSI).

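### The nonparametric fallback for the paired primary CAPS-5 analysis is named as the Wilcoxon rank-sum test, which is a test for two independent samples

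*SAP*

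**What the plan says.** The protocol (12.0 Data Analysis) sets the primary test: "The primary measure will be a paired T-test of CAPS scores from Baseline to Primary Endpoint". It names no nonparametric alternative. The SAP (6.0, 1. Primary Efficacy Analyses) agrees on the test: "The primary efficacy evaluation is a paired t-test of CAPS-5 Total Severity scores at baseline and the primary endpoint (visit 16"). It then adds the fallback: "If the parametric assumptions for t-test analyses are not met, the analogous nonparametric methods will be used (Wilcoxon Rank-Sum").

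The comparison is within one group. Protocol Table 4 assigns CAPS-5 to the PTSD+ participant and not to the CSO participant, and section 5.2.8 does the same for the Primary Assessment. The power statement in Protocol 12.1 is also for a paired design: "estimated power for a within-subject analysis with a significance level of .05 based on a 2-tailed test, is 62"% with 10 participants and an assumed effect size of about 0.8.

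The opening of SAP 6.0 says that the assumptions of any parametric analysis will be examined, and it too offers the rank-sum test as its example of a replacement. Neither document mentions the signed-rank test or gives a criterion for deciding that the assumptions have failed.

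**The concern.** The rank-sum test would treat the 10 baseline scores and the 10 visit 16 scores as coming from 20 unrelated people. The nonparametric analogue of the paired t-test is the Wilcoxon signed-rank test on the within-person changes. The SAP sentence therefore contradicts itself: it promises the analogous method and then names a different one.

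What is at stake is the single primary p-value. If the t-test assumptions are found wanting, the analyst must either run a test that ignores the pairing or depart from the plan on the primary endpoint after seeing the data. A prespecified fallback exists to avoid that choice. When pre-post correlation is positive and changes are roughly symmetric, ignoring the pairing makes the test conservative. A real change can be missed, but false positives do not increase.

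**Working it through.** **Inputs.** From Protocol 12.1: n = 10, effect size 0.8, two-sided alpha 0.05, stated power 62%. The documents do not give the correlation r between baseline and visit 16 scores, the shape of the distribution or the assumption check. These are assumed and varied below.

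**Step 1: the plan's own figure.** For a paired t-test with the effect in SDs of the change, df = 9 and the noncentrality is 0.8 × √10 = 2.530. The noncentral t distribution gives power 61.6%, which reproduces the stated 62%. Other readings do not: the normal approximation gives 71.6%, a one-sided test 75.4%, and two independent groups of 10 give 39.5%. The planned power therefore depends on the pairing.

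**Step 2: power if the fallback is used.** With equal SDs at both visits, the change has SD √(2(1 − r)) in single-visit SDs, so the mean shift is 0.8 × √(2(1 − r)). The rank-sum test sees that shift against the full spread between people. Exact two-sided regions at n = 10 are W ≤ 8 or ≥ 47 for signed-rank (size 4.88%) and U ≤ 23 or ≥ 77 for rank-sum (size 4.33% with independent samples). Simulation used normal scores and 100,000 trials per setting.

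| r | Shift (single-visit SDs) | Rank-sum power | Signed-rank power | Rank-sum type I error |
|---|---|---|---|---|
| 0 | 1.13 | 62% | 60% | 4.2% |
| 0.3 | 0.95 | 47% | 60% | 2.0% |
| 0.5 | 0.80 | 32% | 60% | 0.9% |
| 0.7 | 0.62 | 14% | 60% | 0.2% |
| 0.9 | 0.36 | 1% | 60% | <0.01% |

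Signed-rank type I error is 4.7 to 4.9% throughout.

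**Step 3: power of the whole procedure.** The paired t-test is run unless a Shapiro-Wilk test at 5% on the 10 changes rejects; only then is the fallback used. Scores are √r × a common part plus √(1 − r) × a visit-specific part. Each part is normal, t(3) or centred exponential, so every simulated change is symmetric. There are 20,000 trials per setting and no ties. Cells show power with rank-sum / with signed-rank as the fallback, in %.

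| Scores (check fires) | r = 0 | 0.3 | 0.5 | 0.7 | 0.9 |
|---|---|---|---|---|---|
| Normal (5%) | 61.3 / 61.2 | 61.0 / 61.6 | 60.6 / 61.8 | 59.1 / 61.3 | 58.7 / 61.5 |
| t(3) (15%) | 76.6 / 72.7 | 74.0 / 72.7 | 72.0 / 73.0 | 68.8 / 72.5 | 65.4 / 73.0 |
| Exponential (15%) | 70.7 / 66.7 | 67.6 / 66.2 | 64.8 / 66.0 | 62.5 / 66.2 | 58.5 / 66.1 |

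The loss is about 1 point or less for r up to 0.5, 2 to 4 points at 0.7 and 3 to 8 points at 0.9. In the two non-normal cases with r of 0.3 or less, the text as written gains 1 to 4 points. Type I error of the whole procedure is 3.6 to 5.2% with rank-sum and 4.4 to 5.3% with signed-rank.

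**Step 4: a looser check.** With Shapiro-Wilk at 20%, the fallback fires in 20% of normal and 32 to 34% of non-normal trials. The loss becomes 4 to 5 points at r = 0.5, 9 to 10 at 0.7 and 11 to 18 at 0.9.

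**Step 5: skewed changes.** If the change itself is exponential with mean zero, signed-rank rejects in about 9% of trials and the paired t-test in about 10%. Neither holds 5% as a test of the mean, so no power comparison is made there. Signed-rank tests symmetry about zero, and a skewed change with mean zero does not satisfy that hypothesis.

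**The case against.** The best defence is that the bracket is a slip. The sentence asks for the method analogous to a paired t-test, and a competent analyst would run the signed-rank test. The practical loss is also small, because the fallback is rarely reached under a 5% check. The large losses in Step 2 assume normal scores, for which the fallback would seldom be used, and those in Step 4 need a loose check that the SAP does not specify. The primary test, Hedges' g and the 62% power figure are all unaffected. The protocol already admits a weakness, "suggesting the potential for an underpowered design", and the SAP says of its purpose: "This study is not intended to lead to a registration study".

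All of that limits the consequence, and it stands. It does not make the rule right: the only test named is the wrong one, and the general example at the start of SAP 6.0 points the same way.

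It could also be said that a paired CAPS-5 analysis survives among the secondary analyses: "a one-way repeated-measures ANOVA with post-hoc contrast comparisons will be conducted to test the effects of the treatment on: PTSD CAPS-5". CAPS-5 is scheduled at "Baseline, Endpoint, LTFU 3, 6", with no midpoint, so up to visit 16 that model has two time points and is equivalent to the paired t-test. This gives little protection. It relies on the same assumptions whose failure triggers the fallback, and the general replacement rule in SAP 6.0 covers it too, with no rank analogue named for ANOVA.

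**Conclusion.** The concern holds. The SAP attaches an independent-samples test to a paired primary comparison, and neither document names the paired alternative. It should be corrected because it governs the primary p-value and the correction is nearly free, but the expected effect on the result is small. The sizes rest on n = 10, an effect of 0.8 in SDs of the change, an assumed correlation, an assumed Shapiro-Wilk trigger, symmetric changes and no ties. Within those limits the error costs power when correlation is moderate to high and does not inflate type I error.

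**What to change.** In SAP 6.0, 1. Primary Efficacy Analyses, replace the named fallback with the Wilcoxon signed-rank test on the within-participant change in CAPS-5, using an exact p-value, and state that it assumes roughly symmetric changes. For consistency, say in the opening of SAP 6.0 that rank-sum is the example for independent groups; this is optional. The secondary and long-term models need no change on this account.

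The cost is one test name, one short condition and one SAS procedure call, with no new data. There are two downsides. Signed-rank does not protect the test of mean change when changes are strongly skewed (about 9% rejection in Step 5), and in the non-normal cases with correlation of 0.3 or less it gives up 1 to 4 points of power.
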